**16 LIST OF TABLES, LISTINGS, AND FIGURES****16.1 LIST OF TABLES**

Table Number	Table Title
14.1.1	Summary of Subject Accountability
14.1.2	Summary of Analysis Population Information
14.1.3	Summary of Demographic Data
14.1.4	Summary of PAH History
14.1.5	Summary of Entry Criteria Violations
14.1.6	Summary of Protocol Deviations
14.1.7	Summary of Randomization Information
14.1.8	Summary of Medical History
14.1.9	Summary of Concomitant Medications Ongoing at Baseline
14.1.10	Summary of Concomitant Medications Added During the Study
14.1.11	Summary of Background PAH Therapy Use
14.1.12	Summary of Background PAH Therapy with Total Daily Dosage at Baseline
14.1.13	Summary of Study Drug Dosing and Exposure
14.1.14	Summary of Study Drug Dosing and Exposure by Background PAH Therapy
14.1.15	Summary of Study Drug Treatment Compliance for First 24 Weeks
14.2.1.1	Summary and Analysis of Adjudicated Clinical Worsening Events – ITT Population
14.2.1.2	Summary and Analysis of Adjudicated Clinical Worsening Events – Per-Protocol Population
14.2.1.3	Summary and Analysis of Clinical Worsening Events with Early Termination Treated as Clinical Worsening Event
14.2.1.4	Summary and Analysis of Clinical Worsening Events with Early Termination due to AEs Treated as Clinical Worsening Event
14.2.1.5	Summary and Analysis of Adjudicated Clinical Worsening Events by Subgroups
14.2.1.6	Summary and Analysis of Investigator Reported Clinical Worsening Events
14.2.1.7	Summary and Analysis of Investigator Reported Clinical Worsening Events
14.2.1.8	Summary and Analysis of Death (All Causes) During the Study
14.2.1.9	Summary and Analysis of Death (All Causes) at Study Closure

Table Number	Table Title
14.2.1.10	Summary and Analysis of Hospitalization Due to Worsening PAH
14.2.2.1	Analysis of 6MWD (meter) at Week 24 Using Mixed Model Repeated Measurement (MMRM) – ITT Population
14.2.2.2	Analysis of 6MWD (meter) at Week 24 Using Mixed Model Repeated Measurement (MMRM) – Per-Protocol Population
14.2.2.3	Analysis of 6MWD (meter) at Week 24 Using Mixed Model Repeated Measurement (MMRM) – for Subjects Who Achieve 9 mg Daily Dose
14.2.2.4	Analysis of 6MWD (meter) at Week 48 Using Mixed Model Repeated Measurement (MMRM) – ITT Population
14.2.2.5	Summary and Analysis of 6MWD (meter) at Week 24 – ITT Populatio
14.2.2.6	Summary and Analysis of 6MWD (meter) at Week 24 – Per-Protocol Population
14.2.2.7	Summary and Analysis of 6MWD (meter) at Week 24 with No Imputation for Missing Data
14.2.2.8	Summary and Analysis of 6MWD (meter) at Week 24 Including Data Collected After Termination of Study Drug
14.2.2.9	Summary and Analysis of 6MWD (meter) at Week 24 by Etiology
14.2.2.10	Summary and Analysis of 6MWD (meter) at Week 24 by Baseline WHO Functional Class
14.2.2.11	Summary and Analysis of 6MWD (meter) at Week 24 by Geographic Region
14.2.2.12	Summary and Analysis of 6MWD (meter) at Week 24 by Sex
14.2.2.13	Summary and Analysis of 6MWD (meter) at Week 24 by Age Group
14.2.2.14	Summary and Analysis of 6MWD (meter) at Week 24 by Study Drug Dose
14.2.2.15	Summary and Analysis of 6MWD (meter) at Week 24 by UT-15C Dose Quartile at Week 24
14.2.2.16	Summary and Analysis of 6MWD (meter) at Week 24 by Background PAH Therapy
14.2.2.17	Summary and Analysis of 6MWD (meter) at Week 24 by Baseline 6MWD Category
14.2.2.18	Summary and Analysis of 6MWD (meter) at Weeks 4, 8, 12, 36, and 48
14.2.2.19	Summary of 6MWD (meter) by Visit with Observed Case
14.2.3.1	Summary and Analysis of NT-proBNP (pg/mL) Data at Week 24
14.2.3.2	Summary and Analysis of NT-proBNP (pg/mL) Data at Weeks 12 and 36

Table Number	Table Title
14.2.3.3	Summary and Analysis of NT-proBNP (pg/mL) Data at Weeks 12, 24, and 36 with LOCF Imputation
14.2.3.4	Summary of NT-proBNP (pg/mL) Data by Visit
14.2.3.5	Analysis of NT-proBNP (pg/mL) at Week 24 Using Mixed Model Repeated Measurement (MMRM) – ITT Population
14.2.3.6	Analysis of NT-proBNP (pg/mL) at Week 36 Using Mixed Model Repeated Measurement (MMRM) – ITT Population
14.2.4.1	Summary and Analysis of Borg Dyspnea Score up to Week 48
14.2.4.2	Summary of Borg Dyspnea Score by Visit with Observed Case
14.2.5.1	Summary and Analysis of WHO Functional Class up to Week 48
14.2.5.2	Summary of WHO Functional Class by Visit with Observed Case
14.2.6	Summary and Analysis of Hemodynamic Parameters at Week 24
14.2.7	Summary of Hospitalization Information
14.3.1.1	Overall Summary of Adverse Events
14.3.1.2	Summary of Adverse Events by System Organ Class and Preferred Term
14.3.1.3	Summary of Adverse Events by System Organ Class
14.3.1.4	Summary of Adverse Events by Preferred Term
14.3.1.5	Summary of Deaths
14.3.1.6	Summary of Serious Adverse Events by Preferred Term
14.3.1.7	Summary of Adverse Events Probably or Possibly Related to Study Drug by Preferred Term
14.3.1.8	Summary of Adverse Events Leading to Permanent Discontinuation of Study Drug by Preferred Term
14.3.1.9	Summary of Non-serious Adverse Events by Preferred Term
14.3.1.10	Summary of Adverse Events by Maximum Seriousness and Causality
14.3.1.11	Summary of Adverse Events by Maximum Intensity
14.3.1.12	Summary of Adverse Events by Maximum Intensity and Causality
14.3.1.13	Summary of Adverse Events by Study Drug Dose at Onset
14.3.2.1	List of Deaths
14.3.2.2	Listing of Serious Adverse Events
14.3.2.3	Listing of Adverse Events Leading to Permanent Discontinuation of Study Drug
14.3.4.1	Summary of Clinical Chemistry Data
14.3.4.2	Summary of Clinical Chemistry Shift from Baseline

Table Number	Table Title
14.3.4.3	Summary of Hematology Data
14.3.4.4	Summary of Hematology Shift from Baseline
14.3.4.5	Summary of Urinalysis Data
14.3.5	Summary of Vital Signs
14.3.6.1	Summary of Electrocardiogram Parameters
14.3.6.2	Summary of Electrocardiogram Categorical Results
14.3.7	Summary of Disease Related Events

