6 DRUGS AND DOSING

6.1 DRUG DOSAGE, ADMINISTRATION AND SCHEDULE

The UT-15C tablets are sustained release osmotic tablets. Active treatment is UT-15C tablets provided as 0.125, 0.25, 0.5, 1, and 2.5 mg strengths. The 0.125, 0.25, 0.5, 1, and 2.5 mg tablets are colored blue, green, white, yellow, and pink, respectively. The formulation contains

pharmaceutically acceptable excipients used in other approved drug products. Placebo tablets are identical in size, shape, and color to the respective UT-15C tablets.

Once all entry criteria have been met and random treatment assignment confirmed, the first dose of study drug (0.125 mg) should be taken at the site by the subject immediately after (~10 minutes) consuming food. Oral dosing of study drug will be continued at 0.125 mg TID (every 6 to 8 hours) immediately after (~10 minutes) consuming food. Subjects must be instructed to take the appropriate amount of UT-15C tablets based upon their prescribed dose. Prior to the Week 4 visit, each dose of study drug should be adjusted in 0.125 mg increments every 24 hours as clinically indicated. Following the Week 4 visit throughout the remainder of the study, each dose of study drug may be adjusted in 0.125 or 0.25 mg increments every 24 hours as clinically indicated. The maximum allowable dose of study drug will be 12 mg TID.

Doses of study drug should continue to be increased in the absence of dose-limiting drug-related adverse effects, to ensure that each subject receives the optimal clinical dose throughout the study. [Table 6-1](#) provides a range of doses that may be reasonable targets for a subject to achieve by visit notwithstanding any AEs that limit dose escalation.

Table 6-1 Study Drug Goal Dose Titration Ranges

Study Week	Dose (mg) Three Times Daily
4	0.5 – 1.5
8	1.5 – 2.5
12	2.5 – 3.5
24	5.5 – 6.5

Dose changes should be conducted under appropriate medical supervision in consultation with the study site. Each dose of study drug is not required to be the same during titration. For example, doses of 1.125 mg morning, 1.125 mg afternoon, and 1.25 mg evening, are acceptable during titration. It is recommended that the difference between any of the three doses not exceed 0.125 mg prior to Week 4 or 0.25 mg after Week 4.

At least weekly telephone calls between site personnel and the subject should be made during the first 24 weeks of the study to monitor AEs and make decisions about dose titration. More

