frequent telephone calls may be necessary depending on the frequency of dose titration and to manage AEs or signs and symptoms of disease. If dose titration is considered appropriate, site personnel will instruct the subject to modify their dose. Study drug dosing should be recorded at each study visit between Baseline and Week 24. Dose changes between Baseline and Week 24 will be recorded in source documentation and the subject's eCRF by site personnel. Beyond Week 24, study drug dose will be recorded on the day of Continued Visits (e.g. Weeks 36, 48, etc.) and every 30 days between Continued Visits in source documentation and the eCRF by site personnel. If it becomes necessary for a subject to modify their dose (e.g., due to an AE) without prior instructions from site personnel, the subject should be instructed to contact the site as soon as possible and report any dose changes to site personnel for updating in source documentation and the eCRF as appropriate.

After Week 24, at least monthly telephone calls should be made to continue to monitor AEs and make decisions regarding appropriate dose titrations. More frequent telephone calls may be necessary depending on the frequency of dose titration and to manage AEs or signs and symptoms of disease. Site personnel should record all dose changes in source documentation from Week 24 until Study Termination.

In the event a subject requires to be permanently discontinued from study drug (e.g. as a result of clinical worsening or the subject wishes to withdraw from further participation in the study), the Investigator should conduct the study drug termination assessments and then gradually down titrate the study drug, taking into consideration the subject's clinical condition, current study drug dosing regimen, and previous clinical response to study drug.

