### 12.2 ADVERSE EVENTS

All AEs will be coded using MedDRA and will be listed by treatment group, including all the details on the eCRF page plus an indicator of whether the event was treatment emergent. The AE listings will include the AE verbatim term and its corresponding PT and SOC.

The AE summary tables will be limited to include only treatment-emergent AEs and will be summarized for each treatment group. Treatment-emergent AEs are those AEs with an onset date equal to or after the start date of the study drug. The non-treatment emergent AEs (the AEs that occur after signing the informed consent form, but before receiving study drug, will be listed but will not be included in summary tables.

All summaries will include the number and percentage of subjects experiencing each type of event based on PT and the total number of each type of event, in order of overall frequency and/or SOC. Serious AEs and non-serious AEs will be summarized by PT.

Maximum level of seriousness and intensity occurring during the treatment phase for each AE will be summarized separately and by causality (probable or possible versus not related).

Considering the potential imbalance in treatment exposure, the total number of AEs and the AE rate will be calculated and summarized. The AE rate will be calculated as the total number of AEs divided by the total patient years per treatment group.

Separate listings and summary tables will be provided for all serious adverse events (SAEs), AEs leading to the discontinuation of the study drug, and all deaths during the study.

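### The table of adverse events by dose at onset has no time-at-dose denominator, so its pattern across doses cannot be read as dose-response (minor)

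*SAP*

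**What the plan says.** SAP 16.1 lists Table 14.3.1.13, "Summary of Adverse Events by Study Drug Dose at Onset". Only the title is given: no dose bands and no denominator.

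SAP 12.2 sets the general content of adverse event (AE) tables: "All summaries will include the number and percentage of subjects experiencing each type of event based on PT", together with the total number of events of each type. Because exposure may differ between arms, it adds one exposure-adjusted figure: "The AE rate will be calculated as the total number of AEs divided by the total patient years per treatment group". SAP 12.1 plans doses by visit, maximum dose, overall duration of exposure and a listing of dose changes. It plans no summary of time spent in each dose band.

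Protocol 6.1 starts every subject at 0.125 mg TID and titrates upward, and "The maximum allowable dose of study drug will be 12 mg TID". Table 6-1 gives goal ranges of 0.5–1.5, 1.5–2.5, 2.5–3.5 and 5.5–6.5 mg TID at Weeks 4, 8, 12 and 24. Escalation may slow, and doses may be reduced, for intolerable AEs.

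On contact, protocol 6.1 says "At least weekly telephone calls between site personnel and the subject should be made during the first 24 weeks of the study to monitor AEs". For the later period the same section says "After Week 24, at least monthly telephone calls should be made to continue to monitor AEs". Both are minimums: "More frequent telephone calls may be necessary depending on the frequency of dose titration and to manage AEs".

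**The concern.** A table of AEs by dose at onset invites the question of whether AEs become more frequent as the dose rises. Counts and percentages of subjects cannot answer it, for three reasons.

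- **Time at dose.** The number of events recorded at a dose depends on how long subjects stayed there. Everyone passes through the low doses, perhaps within weeks. Some then spend years at higher doses, and others never reach them.
- **Selection.** Dose responds to AEs, so time at high dose is contributed mainly by subjects who tolerate the drug.
- **Contact.** The minimum call frequency falls at Week 24, so low-dose time early in the study is observed more closely than most later time.

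The SAP already accepts that unequal exposure between arms calls for a rate. Exposure is likely to be much more unequal between doses, and there no rate is planned. At stake is the reading of one descriptive table, including any impression of which doses are well tolerated.

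**Working it through.** The documents give no figure for this table, so there is none to reproduce. The calculation below shows what an inert tablet would produce.

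**Inputs from the documents.** UT-15C median time to event 32/0.62 = 51.6 months, accrual over 36 months and 10% drop-out (protocol 10.2); duration 48 months (protocol 3.5); dose cut of 9 mg total daily dose (SAP 8.2 and 10.2.1.1).

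**Assumptions.** Uniform accrual; constant drop-out hazard; a constant true AE rate at every dose. In the first scenario all subjects follow the midpoints of Table 6-1, reaching 3 mg TID (9 mg per day) at Week 12.

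**Person-time.**
- Exit hazard λ = ln 2/51.6 − ln(0.9)/48 = 0.01343 + 0.00220 = 0.01563 per month.
- Mean person-months up to time T = (1 − e^(−λT))/λ. Week 12 is 2.76 months and gives 2.70. Week 24 is 5.52 months and gives 5.29.
- Averaged over administrative follow-up of 12 to 48 months, the total is 23.42 months.
- Shares: Weeks 0–12, 2.70/23.42 = 11.5%; Weeks 12–24, 2.59/23.42 = 11.0%; after Week 24, 18.13/23.42 = 77.4%.

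**Ratio of event counts, at or above versus below 9 mg per day, with no dose effect and full capture.**
- All reach 9 mg per day at Week 12: (2.59 + 18.13)/2.70 = 7.7.
- All reach it only at Week 24: 18.13/5.29 = 3.4.
- A fraction q reach it at Week 12 and the rest never do: 0.885q/(1 − 0.885q). With q = 0.5 this is 0.4425/0.5575 = 0.8.
- Stopping at 205 events instead of at 48 months shortens follow-up. The Weeks 0–12 share in the UT-15C arm becomes about 13.2% with 610 subjects and 17.6% with 850. The first ratio becomes 86.8/13.2 = 6.6 or 82.4/17.6 = 4.7.

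The null pattern can therefore run steeply upward or mildly downward, depending only on the titration path.

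**Difference between arms within a dose band.** In TDE-PH-308 (protocol 1.2.4) the mean maximum dose was 3.1 ± 1.9 mg BID on UT-15C and 6.1 ± 3.6 mg BID on placebo. At 4.5 mg BID (9 mg per day), a normal shape gives z = (4.5 − 3.1)/1.9 = 0.74 and z = (4.5 − 6.1)/3.6 = −0.44, so 23% and 67% would reach the cut. A lognormal shape gives 17% and 61%. Percentages based on all subjects in each arm would then differ about threefold in who could have an event in the upper band. That was a 16-week BID study, so the size here will differ.

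**Contact.** Calls fall from 12 to 84/30 = 2.8 per 12 weeks. With one visit in each period, contacts fall from 13 to 3.8. Let r be the share of AEs captured after Week 24 relative to before (an assumption). In the first scenario:

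| r | Count ratio (2.59 + 18.13r)/2.70 | Rate ratio (2.59 + 18.13r)/20.72 |
|---|---|---|
| 1.0 | 7.7 | 1.00 |
| 0.9 | 7.0 | 0.91 |
| 0.75 | 6.0 | 0.78 |
| 0.5 | 4.3 | 0.56 |

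Dividing by patient-years removes the time-at-dose artefact. It leaves whatever contact effect exists, which is the reason for a supportive split at Week 24.

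**The case against.** A reader might infer that the contact schedule itself sets the dose trend. The documents do not support that. In the first scenario time at dose is the larger force and works in the opposite direction: halving capture after Week 24 only lowers the count ratio from 7.7 to 4.3. Calls are minimums, visits with AE assessment continue every 12 weeks, and AEs carry onset dates (protocol 9.2), so a monthly call can still pick up earlier events. The loss of capture is unknown and may be small.

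Nor can low doses be equated with the weekly-contact period. Table 6-1 gives targets. Achieved doses in earlier studies were lower: the extension study's mean was 3.9 mg BID at one year, or 7.8 mg per day, against a Week 24 goal of 16.5 to 19.5 mg per day. TID dosing may allow higher doses, but much lower-dose time could still fall after Week 24.

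Three further points are fair. Because only a title exists, the count-and-percentage content is inferred from the general rule in SAP 12.2, which sets minimum content. AE tables are already presented by arm, so a placebo column should be present. The table carries no test or decision rule, and neither document says that titration advice will be drawn from it.

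The missing denominator stands. A placebo column of counts or percentages does not supply it, because the arms may titrate differently.

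**Conclusion.** The point holds as a minor one. As planned, Table 14.3.1.13 mixes dose with time at dose and with selection of tolerant subjects, and nothing else in the SAP lets a reader separate them. For an inert tablet the count ratio at the 9 mg per day cut ranges from about 0.8 to 7.7 across the titration paths shown. Those paths, the constant AE rate and the choice of cut are illustrative assumptions; the follow-up inputs are the protocol's own. Reduced contact after Week 24 is a secondary distortion of unknown size.

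It would be wrong to infer that the overall AE comparison between arms is compromised. Both arms follow the same blinded contact schedule. Even if reporting were 2 to 5 times higher in the first 24 weeks (an assumption), the pooled AE rate ratio under no effect would stay at 0.96 to 0.99, so that rate need not be split. The primary analysis is unaffected.

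**What to change.** In SAP 12.2, specify Table 14.3.1.13 as follows:

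- Define the dose bands, for example with the SAP's existing cut of 9 mg total daily dose.
- In each band and arm, give the number of events, the patient-years spent in the band, and events per patient-year. Show placebo by nominal tablet dose alongside.
- As a supportive display, show the same rates separately up to and after Week 24.
- Add a footnote that dose was adjusted according to tolerability, so the rates remain descriptive. Patient-years do not remove selection.

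The cost is SAP wording and one derived time-at-dose variable from dosing data already collected. Up to Week 24 dose changes go into the eCRF. After that the protocol requires eCRF doses at Continued Visits and every 30 days between them, so band times will be approximate unless the dated dose changes that SAP 12.1 expects to list are available.

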## 16.2 LIST OF LISTINGS

Listing Number	Listing Title
16.2.1.1	Subject Dispositions
16.2.1.2	Subject Accountability
16.2.2	Protocol Deviations
16.2.3.1	Subject Randomization
16.2.3.2	Analysis Population Information
16.2.3.3	Entry Criteria
16.2.4.1	Demographics
16.2.4.2	PAH History
16.2.4.3	Medical History
16.2.4.4	Concomitant Medications
16.2.5.1	Study Drug Dosing
16.2.5.2	Compliance for First 24 Weeks of Treatment
16.2.5.3	Background PAH Medication History
16.2.5.4	Change to ERA, PDE5-I, or sGC Stimulator Dosing
16.2.6.1	Clinical Worsening Events
16.2.6.2	Time to Clinical Worsening Events
16.2.6.3	6MWT and Borg Dyspnea Score Data
16.2.6.4	6MWT Information with Imputed Data up to Week 48
16.2.6.5	WHO Functional Class for PAH
16.2.6.6	WHO Functional Class with Imputed Data up to Week 48
16.2.6.7	Plasma NT-proBNP (pmol/L)
16.2.6.8	Plasma NT-proBNP (pmol/L) with Imputed Data up to Week 36
16.2.6.9	Hemodynamic Measurements

Listing Number	Listing Title
16.2.6.10	Hospitalizations
16.2.6.11	Death Records
16.2.6.12	Disease Related Events
16.2.7	Adverse Events
16.2.8.1	Laboratory Results – Clinical Chemistry
16.2.8.2	Laboratory Results – Hematology
16.2.8.3	Laboratory Results – Urinalysis
16.2.8.4	Pregnancy Test Results (Female Subjects Only)
16.2.8.5	Vital Signs
16.2.8.6	Electrocardiogram Results

### 16.3 LIST OF FIGURES

Figure Number	Figure Title
14.2.1.1	Kaplan-Meier Plot of Time to Adjudicated Clinical Worsening Events
14.2.1.2	Kaplan-Meier Plot of Time to Investigator Reported Clinical Worsening Events
14.2.1.3	Kaplan-Meier Plot of Time to Death
14.2.1.4	Kaplan-Meier Plot of Time to Death at the Study Closure
14.2.1.5	Kaplan-Meier Plot of Hospitalization Due to PAH
14.2.1.6	Forest Plot on Subgroup Analyses of Time to Adjudicated Clinical Worsening Events
14.2.2.1	Plot of 6MWD at Week 24 By UT-15C Drug Dose
14.2.2.2	Forest Plot on Subgroup Analyses of 6MWD (meter) at Week 24
14.2.3	Plot of the Combined 6MWD and Borg Dyspnea Score Ranks at Week 24
